#### **7.6.11.2 Time-to onset of other events of special interest**

Time-to onset of the following specific events will be summarized for each category of other events of special interest for treated subjects who experienced at least one event from the category, reporting median, min, and max:

- Time-to onset of any grade other events of special interest by treatment group
- Time-to onset of grade 3 to 5 other events of special interest by treatment group
- Time-to onset of any grade drug-related other events of special interest by treatment group
- Time-to onset of grade 3 to 5 drug-related other events of special interest by treatment group
- Time-to onset of any grade other events of special interest where immune modulating medication was initiated, by treatment group.
- Time-to onset of grade 3 to 5 other events of special interest where immune modulating medication was initiated, by treatment group.

See time-to onset definition subsection of [Appendix 1](#) for additional details. The analyses will be conducted using the 30-day safety window, and some will be repeated using the 100-day safety window.

#### **7.6.11.3 Time-to resolution of other events of special interest**

Time to resolution of the following specific events will be summarized separately for each category.

- Time-to resolution of any grade other events of special interest by treatment group
- Time-to resolution of grade 3 to 5 other events of special interest by treatment group
- Time-to resolution of any grade drug-related other events of special interest by treatment group

- Time-to resolution of grade 3 to 5 drug-related other events of special interest by treatment group
- Time-to resolution of any grade other events of special interest where immune modulating medication was initiated, by treatment group.
- Time-to resolution of grade 3 to 5 other events of special interest where immune modulating medication was initiated, by treatment group.

Time-to resolution analyses are restricted to treated subjects who experienced the specific events. The analyses will be conducted using the 30-day safety window, and some will be repeated using the 100-day safety window.

See time-to resolution definition subsection of [Appendix 1](#) for additional details.

#### **7.6.11.4 Immune Modulating Medication for other events of special interest**

For each category of other events of special interest, the following will be reported for each treatment group:

- Percentage of subjects who received immune modulating concomitant medication for management of other events of special interest in the category among subjects who experienced at least one other events of special interest in the category.
- The total medication treatment duration, duration of high dose of corticosteroid and tapering duration (summary statistics)

These analyses will be performed on any other events of special interest, grade 3-5 other events of special interest.

The analysis will be conducted using the 100-day safety window.

### **7.6.12 Laboratory Parameters**

#### **7.6.12.1 Hematology**

See Section 7.6.9.1 of Core Safety SAP

#### **7.6.12.2 Serum Chemistry**

See Section 7.6.9.2 of Core Safety SAP

#### **7.6.12.3 Electrolytes**

See Section 7.6.9.3 of Core Safety SAP

#### **7.6.12.4 Additional Analyses**

See Section 7.6.9.4 of Core Safety SAP

### **7.6.13 Vital Signs and Pulse Oximetry**

See Section 7.6.10 of Core Safety SAP

**7.6.14 Immunogenicity Analyses**

Not applicable

**7.6.15 Pregnancy**

See Section 7.6.12 of Core Safety SAP

**7.6.16 Clinical Safety Program (CSP)**

Not applicable

**7.6.17 Adverse Events By Subgroup**

See Section 7.6.14 of Core Safety SAP

[Redacted content]

• [REDACTED]  
[REDACTED]  
[REDACTED]

### 7.8 Outcomes Research Analyses

Descriptive summary statistics of Patient Reported Outcomes will be presented at baseline and each on-study time point, unless otherwise specified. Mean changes from baseline for each of the 2 scales will be calculated for each subject at each on-study time point. In addition, subject compliance will be described per time point by the proportion of subjects who filled out the QoL assessments over the numbers of subject known to be alive and eligible for assessment at these time points. The analysis will be performed for all treated subjects and in Groups 1, 2, and 3.

[REDACTED]

[REDACTED]

[REDACTED]

[REDACTED]

[REDACTED]

[REDACTED]

[REDACTED]

[REDACTED]

[REDACTED]

[REDACTED]

[REDACTED]

[REDACTED]

[REDACTED]

[REDACTED]

[REDACTED]

[REDACTED]

[REDACTED]

[REDACTED]

[REDACTED]

[REDACTED]

[REDACTED]

[REDACTED]

[REDACTED]

[REDACTED]

[REDACTED]

[REDACTED]

[REDACTED]

[REDACTED]

### 7.9 Health Care Resource Utilization

Hospitalization rate based on person year will be summarized in table. Descriptive summary statistics of length of stay will be presented at baseline and each on-study time point, unless otherwise specified. The analysis will be performed for all treated subjects and in Groups 1, 2, and 3.

All hospitalization will be presented in a listing.

## 8 CONVENTIONS

The following conventions may be used for imputing partial dates for analyses requiring dates:

For missing and partial adverse event onset dates, imputation will be performed using the Adverse Event Domain Requirements Specification. Missing and partial Non-Study Medication Domain dates will be imputed using the derivation algorithm described in BMS Non-Study Medication Domain Requirements Specification.

For death dates, the following conventions will be used for imputing partial dates:

- If only the day of the month is missing, the 1st of the month will be used to replace the missing day. The imputed date will be compared to the last known alive date +1 day and the maximum will be considered as the death date.
- If the month or the year is missing, the death date will be imputed as the last known alive date + 1 day
- If the date is completely missing but the reason for death is present the death date will be imputed as the last known alive date + 1 day

For date of progression, the following conventions will be used for imputing partial dates:

- If only the day of the month is missing, the 1st of the month will be used to replace the missing day.

- If the day and month are missing or a date is completely missing, it will be considered as missing.
- \* In case, the date of death is present and complete, the imputed progression date will be compared to the date of death. The minimum of the imputed progression date and date of death will be considered as the date of progression.

The following conversion factors will be used to convert days to months or years: 1 month = 30.4375 days and 1 year = 365.25 days.

Duration (e.g. time from first diagnosis of NSCLC to first dosing date, duration response, and time to response) will be calculated as follows:

Duration = (Last date - first date + 1)

All statistical analyses will be carried out using SAS (Statistical Analysis System software, SAS Institute, North Carolina, USA) unless otherwise noted.

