### **3.6.2 Lost to Follow-Up**

All reasonable efforts must be made to locate subjects to determine and report their ongoing status. This includes follow-up with persons authorized by the subject as noted above. Lost to follow-up is defined by the inability to reach the subject after a minimum of three documented phone calls, faxes, or emails as well as lack of response by subject to one registered mail letter. All attempts should be documented in the subject's medical records. If it is determined that the subject has died, the site will use permissible local methods to obtain the date and cause of death.

If investigator's use of third-party representative to assist in the follow-up portion of the study has been included in the subject's informed consent, then the investigator may use a Sponsor-retained third-party representative to assist site staff with obtaining subject's contact information or other public vital status data necessary to complete the follow-up portion of the study. The site staff and representative will consult publicly available sources, such as public health registries and databases, in order to obtain updated contact information. If after all attempts, the subject remains lost to follow-up, then the last known alive date as determined by the investigator should be reported and documented in the subject's medical records.

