Patient-Reported Outcome Measurements	X			Prior to any study-related procedures: FKSI-19, and EQ-5D
Health Resource Utilization	X			Prior to any study-related procedures

Table 5.1-3: Follow-up Procedural Outline (CA209374)			
Procedure	Follow-up Visit 1 (X01) and Visit 2 (X02).	Follow-up after Visit 2 (X02)	Notes
			Follow up Visit (X01) = 30 days from last dose +/-5 days, or may be on date of discontinuation +/-5 days if the date of discontinuation is more than 35 days after last dose. Follow up Visit 2 (X02) = 100-114 days from last dose.
Vital Signs	X		
Physical measurements	X		Includes performance status (Karnofsky)
Adverse Events Assessment	X	X*	*Beyond 100-114 days from the last dose of study therapy, subjects will be followed for ongoing drug-related AEs until resolved, return to baseline or deemed irreversible, or until lost to follow-up or withdrawal of study consent.
Laboratory Tests	X		CBC with differential, serum chemistry (BUN or serum urea level, serum creatinine, albumin, sodium, potassium, calcium, magnesium, phosphate, chloride, bicarbonate, glucose), liver function (AST, ALT, total bilirubin, alkaline phosphatase, LDH), thyroid function (TSH, reflex to free T3 and free T4 if abnormal result)
Review of concomitant medications	X		
Pregnancy testing	X		Serum or urine
Collection of Survival Information	X	X	Every 3 months until death, lost to follow-up, or withdrawal of study consent for 5 years following start of therapy. May be performed by phone contact or office visit.
Radiographic Tumor Assessment	X	X	For subjects who discontinue study treatment for reasons other than PD, follow up scans (or MRIs when appropriate) should be performed every 8 weeks ( $\pm$ 5 days) for the first 13 months then every 12 weeks $\pm$ 1 week until PD, death, lost to follow-up, or withdrawal of consent. Radiographic assessments should not be delayed until the X01 or X02.

Table 5.1-3: Follow-up Procedural Outline (CA209374)			
Procedure	Follow-up Visit 1 (X01) and Visit 2 (X02).	Follow-up after Visit 2 (X02)	Notes
Patient Reported Outcomes			
FKSI-19 and EQ-5D	X	X	At X01 and X02 and then every 3 months for the first 12 months, then every 6 months thereafter, as permitted by local IRB. Assessments can be conducted by phone or mail.
Healthcare Resource Utilization	X	X	To be collected in alignment with PRO's above (, FKSI-19 and EQ-5D). Assessments can be conducted by phone or mail.

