## **7.5 Efficacy**

### **7.5.1 OS**

#### **7.5.1.1 Survival Analysis**

The OS curve will be estimated using the Kaplan-Meier (KM) product-limit method, along with the median and its 95% CI using Brookmeyer and Crowley method. Survival rates at different

time points (at 6, 12, 18, 24, and 36 months) will also be estimated using KM estimates from the OS curve. Associated two-sided 95% CIs will be calculated using the Greenwood formula. This analysis will be performed for all treated subjects and all subjects in Groups 1, 2, and 3.

The status of subjects who are censored in the OS Kaplan-Meier analysis will be tabulated for Group 1, 2, and 3, using following categories:

- on-study (on-treatment and not progressed, on-treatment progressed, in follow-up);
- off-study: (lost to follow-up, withdraw consent, etc.).

A by subject listing of overall survival will be produced.

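### SAP 8 discards a recorded year of death when the month is missing, so some deaths are imputed into a year the record rules out

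*SAP*

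**What the plan says.** SAP 8 has three death-date rules.

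- Only the day missing: the first of the recorded month is taken, and then "The imputed date will be compared to the last known alive date +1 day and the maximum will be considered as the death date".
- Month or year missing: "If the month or the year is missing, the death date will be imputed as the last known alive date + 1 day".
- Date wholly missing but a reason for death given: the same imputation as in the second rule.

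The section opens permissively, "The following conventions may be used for imputing partial dates for analyses requiring dates", but the line introducing the death-date bullets is unconditional and no alternative is given. Nothing else in the visible SAP or protocol checks the imputed date against a recorded year.

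The date is used in SAP 7.5.1.1: "The OS curve will be estimated using the Kaplan-Meier (KM) product-limit method". That section also asks for the median and for rates from 6 to 36 months, in all treated subjects and in Groups 1 to 3. Protocol Table 5.1-3 schedules survival contact as follows: "Every 3 months until death, lost to follow-up, or withdrawal of study consent for 5 years following start of therapy". For subjects lost to follow-up, Protocol 3.6.2 says: "If it is determined that the subject has died, the site will use permissible local methods to obtain the date and cause of death".

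**The concern.** The first two rules follow different logic. With the day missing, the SAP keeps what is known (month and year) and lets the last-alive date act only as a lower bound. With the month missing, it drops the known year and treats the record as if no date existed.

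The result can contradict the subject's own data: a person recorded as dying in 2019 can enter the analysis as dying in 2017. The error runs one way only, because the imputed date is the earliest that the last-alive date allows. It can shorten OS and never lengthen it. At stake is the accuracy of the descriptive OS estimates, most visibly in Group 3, which is planned at about 25 subjects.

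**Working it through.** No stated sample size, power or confidence interval depends on this rule, so there is no plan figure to reproduce. The check applies the SAP rule and the missing-day logic extended to years to the same records.

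**Rules compared**
- SAP rule: death = A + 1 day, where A is the date last known alive.
- Extended rule: death = the later of 1 January of the recorded year and A + 1 day.
- Conversion, from SAP 8: "1 month = 30.4375 days and 1 year = 365.25 days". SAP 8 also defines a duration as last date minus first date plus 1.

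**Example records** (dates are illustrative assumptions)

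| Last alive | Recorded year | SAP date | Extended rule | Difference |
|---|---|---|---|---|
| 10 Mar 2017 | 2017 | 11 Mar 2017 | 11 Mar 2017 | 0 days |
| 20 Dec 2017 | 2018 | 21 Dec 2017 | 1 Jan 2018 | 11 days |
| 15 Oct 2017 | 2018 | 16 Oct 2017 | 1 Jan 2018 | 77 days |
| 1 Nov 2016 | 2018 | 2 Nov 2016 | 1 Jan 2018 | 425 days |
| 10 Feb 2017 | 2019 | 11 Feb 2017 | 1 Jan 2019 | 689 days |

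The last row is 689 / 30.4375 = 22.6 months. In the fourth row, with first dose assumed on 1 Jun 2016, OS is 155 / 30.4375 = 5.09 months under the SAP rule and 580 / 30.4375 = 19.06 months under the extended rule. The first row shows that matching years give no difference.

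**How often a year-only death lands in the wrong year.** Assume deaths are uniform over a year of 365.25 days and the time since last known alive is uniform on 0 to G days. Then:
- share placed in an earlier year = G / (2 × 365.25);
- mean shortfall among those, measured to 1 January = G/3 − 1 days;
- largest shortfall = about G − 1 days.

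| G | Share | Mean shortfall | Largest |
|---|---|---|---|
| 91 (3-monthly contact) | 91/730.5 = 12.5% | 29.3 days | about 90 days |
| 182 (assumed missed contact) | 182/730.5 = 24.9% | 59.7 days | about 181 days |
| 365 (assumed long gap) | 365/730.5 = 50.0% | 120.7 days | about 364 days |

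A simulation of 1,000,000 deaths under the same assumptions agrees: 12.5%, 25.0% and 50.0%, with mean shortfalls of 29.3, 59.7 and 120.5 days.

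**Effect on the curve.** With no earlier censoring, one misplaced death lowers the Kaplan-Meier curve by 1/150 = 0.7 percentage points overall, or 1/25 = 4 points in Group 3. The drop applies only between the imputed date and the true date of death.

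**Number affected.** The documents give no count. If 0 to 3 of 150 subjects had a year-only death date (an assumption), then on the 3-monthly schedule 0 to 3 × 0.125 = about 0.4 subjects would be placed in the wrong year.

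**The case against.** The strongest reply is that this hardly matters. The primary endpoint is adverse-event incidence, and the visible secondary endpoints describe those events and their management. OS is a single-arm descriptive estimate with no test, and an early death date errs on the conservative side. The proposed date is itself an earliest-possible convention. Under the assumptions above with G = 91, the average shortfall against the true date, over all year-only deaths, falls only from 44.5 to 40.8 days (with G = 365, from 181.5 to 121.3). All of this stands. It limits the importance of the point but does not justify a date the record excludes.

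Several stronger readings are tempting, and the documents do not support them.

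- **Every year-only death is affected.** When the recorded year equals the last-alive year, the two rules give the same date.
- **An error near two years is typical.** The 22.6-month example needs almost two years with no alive date, despite 3-monthly contact and active tracing.
- **The early part of the OS curve is lowered.** The curve is lowered only between the imputed and true dates, wherever in the 5 years they fall.
- **Tracing will produce year-only dates.** Protocol 3.6.2 says "The site staff and representative will consult publicly available sources, such as public health registries and databases", but that sentence concerns updated contact information. Sections 3.6.1 and 3.6.2 do allow searches for vital status, so a partial date after a long gap is possible. Nothing says it is likely.
- **The progression-date rule has the same flaw.** First-of-month imputation could precede an earlier scan only if both fell in one calendar month. Scheduled scans are at least 42 days apart (Week 9 to Week 15), and the first is no earlier than Week 7, 49 days after first dose. The problem would need an off-schedule assessment. Part of the SAP efficacy text is also redacted, so a missing lower bound cannot be established.

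**Conclusion.** The point holds as a minor error in a stated rule. When the month is missing and the recorded year of death is later than the last-alive year, SAP 8 imputes a date that the record contradicts, and OS for that subject is too short. The size is at most about 90 days per affected death if contacts run to schedule, and more only after missed contacts or loss to follow-up.

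The 12.5% share and 29-day mean rest on the uniform assumptions above. The number of year-only deaths is unknown and probably very small. The primary endpoint does not change, and no visible secondary endpoint is shown to change. The date could also reach the landmark survival analysis in SAP 7.5.1.4, which excludes subjects who die before the landmark. A subject long out of contact may be excluded there as off protocol anyway, so no separate claim is made.

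**What to change.** Replace the second death-date rule in SAP 8 with two cases:

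- year known, month missing: use the later of 1 January of that year and the day after the subject was last known alive;
- year missing: keep the day after the subject was last known alive.

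This parallels the existing missing-day rule. It costs one sentence in the SAP and one condition in the date derivation. It needs no new data collection and no change to the protocol, the sample size or the primary analysis. The progression-date convention needs no change on this ground.

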## **7 STATISTICAL ANALYSES**

### **7.1 General Methods**

Unless otherwise noted, the bulleted titles in the following subsections describe tabulations of discrete variables, by the frequency and proportion of subjects falling into each category. Percentages given in these tables will be rounded and, therefore, may not always sum to 100%. Continuous variables will be summarized using the mean, standard deviation, median, minimum and maximum values.

Time to event distribution will be estimated using Kaplan Meier techniques. This will be done for endpoints PFS-1, OS and DOR. Median survival time along with 95% CI will be constructed based on a log-log transformed CI for the survivor function  $S(t)^{4,5}$ . Rates at fixed time points will be derived from the Kaplan Meier estimate and corresponding confidence interval will be derived based on Greenwood formula for variance derivation and on log-log transformation applied on the survivor function  $S(t)^7$ .

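### SAP 8 sets no lower bound on an imputed progression date and leaves a year-only progression undated, with no visible rule for counting it

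*SAP*

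**What the plan says.** SAP Section 8 opens in permissive terms: "The following conventions may be used for imputing partial dates for analyses requiring dates". The lines that introduce the death-date and progression-date rules are worded as firm commitments.

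For progression there are three rules:

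- Day missing: "If only the day of the month is missing, the 1st of the month will be used to replace the missing day".
- Day and month missing, or the whole date missing: "If the day and month are missing or a date is completely missing, it will be considered as missing".
- Where a complete death date exists: "The minimum of the imputed progression date and date of death will be considered as the date of progression".

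For death, the same section uses the 1st of the month when the day is missing, then adds a floor: "The imputed date will be compared to the last known alive date +1 day and the maximum will be considered as the death date". When more is missing, a date is still assigned: "If the month or the year is missing, the death date will be imputed as the last known alive date + 1 day".

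SAP Section 7.1 names the Kaplan-Meier endpoints: "This will be done for endpoints PFS-1, OS and DOR". PFS-1 and DOR use the progression date; OS does not. The text that would define PFS-1 and DOR and their censoring is redacted or not visible.

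**The concern.** Two gaps appear when the death and progression rules are read side by side.

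The first is that an imputed progression date has a ceiling (death) but no floor. Nothing stops the 1st of the month from falling on or before an assessment that showed no progression, or before first dose. The subject's own record rules such a date out, and the resulting duration can be negative.

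The second is that a progression known to the year only has no date. A Kaplan-Meier event needs one, and the visible text does not say whether the subject is counted as an event at death, censored, or handled in some other way. If death is substituted, the time is too long. If a known progressor is censored, an event is lost because of the outcome itself. Either way the progression-based curve tends to look too favourable.

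Only PFS-1 and DOR are at stake. The primary endpoint (incidence of high-grade IMAEs), the visible secondary endpoints (IMAE outcomes and management) and OS do not use this date.

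**Working it through.** The plan states no figure on this point, so there is none to reproduce. The check applies its rules to dates.

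**1. Rules side by side (SAP 8)**

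| Missing part | Death date | Progression date |
|---|---|---|
| Day | later of the 1st of the month and the day after last known alive | 1st of the month |
| Day and month | day after last known alive | left missing |
| Month only | day after last known alive | not addressed |
| Whole date | day after last known alive, if a reason for death is recorded | left missing |
| Lower bound | day after last known alive | none |
| Upper bound | none stated | complete death date |

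**2. How often the 1st-of-month date is impossible.** Each calendar day of 2016 to 2018 (1,096 days) was taken in turn as the last progression-free visit, with true progression a fixed number of days later and its day missing. Over these days the rule moves a date earlier by 14.7 days on average, at most 30.

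| Days from progression-free visit to true progression | Imputed date on or before that visit |
|---|---|
| 7 | 77% |
| 14 | 54% |
| 21 | 31% |
| 28 | 8% |
| 35 or more | 0% |

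**3. Which progressions can be that close.** Protocol 5.4.1 puts scans at 8-week intervals, ±1 week, and later at 12-week intervals.

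- Smallest gap between scheduled tumor scans: 56 − 7 − 7 = 42 days.
- Earliest first scan: 56 − 7 = 49 days after first dose.
- Follow-up scans with the ±5 day window of Table 5.1-3: 56 − 5 − 5 = 46 days.

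All exceed 35 days, so progression found at scheduled tumor scans cannot give an impossible date. These can:

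- an unscheduled scan;
- a brain surveillance scan (Protocol 5.4.1, about every 12 weeks or sooner, for subjects with a history of brain metastasis). A week-8 body scan and a week-12 brain scan are 28 days apart, or 21 if the body scan is a week late;
- palliative bone or brain radiation, which Protocol 3.4.3.1 and 3.4.3.2 count as progression whenever it occurs.

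**4. Two illustrations (invented 2017 dates).** These use the SAP's duration rule, last date − first date + 1; applying it to PFS-1 is an assumption.

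- Case A: first dose 20 January, true progression 28 January (day 9), day missing. Imputed 1 January: −19 + 1 = −18 days. With a floor at the day after first dose: 2 days.
- Case B: first dose 2 January, progression-free scan 10 May (day 129), true progression 28 May (day 147), day missing. Imputed 1 May: day 120, before the progression-free scan. With a floor at the day after that scan: day 130.

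**5. Year-only progression (invented dates).** First dose 1 September 2016, last progression-free scan 20 December 2016, progression recorded only as 2017, death 10 June 2018.

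- Interval the record allows, 1 January to 31 December 2017: days 123 to 487 (divided by 30.4375, 4.0 to 16.0 months).
- If death is substituted (assumption): an event at 648 days (21.3 months), at least 648 − 487 = 161 days too late.
- If censored at the last progression-free scan (assumption): a censored 111 days and no event.

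**6. Population effect, death-substitution branch only.** Let a fraction p of subjects take their OS time in place of their PFS time: S(t) = (1 − p)·0.5^(t/m_PFS) + p·0.5^(t/m_OS). Assume p = 1 to 5%, median PFS 4 or 6 months and median OS 20 to 25 months; the documents give none of these. Median PFS moves from 4 to 4.04–4.24 months, or from 6 to 6.05–6.31 months, a rise of about 1 to 6%. The 12-month rate moves from 12.5% to 13.0–15.5%, or from 25.0% to 25.4–27.3%, a rise of 0.4 to 3.0 points.

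**The case against.** The strongest reply is that the SAP sets the date to missing, not the event. A reader might infer that a documented progression is erased, but the text does not say so. How the subject is counted depends on PFS-1 and DOR definitions that are redacted and cannot be called absent. This stands. So does its corollary: the 648-day result is not what the plan gives. The minimum rule compares an imputed progression date with death, and here no date has been imputed, so the rule need not apply.

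A reader might also infer that PFS-1 and DOR are overstated overall. The documents do not support that, because the 1st-of-month rule moves dates earlier and shortens them. The net direction is not established.

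The impossible dates need both a partial date and an off-schedule progression. For focal palliative radiation to bone, source records must hold the treatment dates (Protocol 3.4.3.1), which makes a partial date less likely. It is also tempting to expect partial dates from telephone follow-up. Table 5.1-3 allows telephone contact for survival, patient-reported outcomes and resource use, and follows progression by imaging, so that explanation has no support.

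The section's opening is permissive, but the progression rules are introduced as firm, so this does not remove the point. Finally, dating a year-only event at the earliest allowed day is a convention, not a correction. In step 5 it could be wrong by up to 487 − 123 = 364 days the other way, so the fix pairs it with a sensitivity analysis.

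**Conclusion.** The point holds in limited form. The 1st-of-month rule has no floor and can give a progression date that the record contradicts, although the death rule in the same section guards against the equivalent error. A progression with unknown month has no date, and the visible text does not say how it is counted.

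The first part follows from the stated rule and needs no assumption beyond a partial date on an off-schedule progression. The second is a request to state the rule. That curves would be too favourable is conditional on death substitution or censoring, and the 1 to 6% shift in the median rests on death substitution with assumed medians and frequencies. The documents do not give the frequency of partial dates, so the true size is unknown and probably small. This is worth correcting, but it does not threaten the study's conclusions on IMAEs or OS.

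**What to change.** Amend the progression-date rules in SAP 8:

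- **Day missing:** use the later of the 1st of the month and the day after the last tumor assessment without progression (or the day after first dose if there is no such assessment), capped at death.
- **Month or whole date missing, progression documented:** keep it as an event dated within the interval the record allows. For example, date it no earlier than the day after the last progression-free assessment and within the known year, capped at death. Flag these subjects, and repeat the analysis with the latest allowed date.
- **Cross-reference:** state in the PFS-1 and DOR definitions that these rules apply, so that an undated progression is not left to the programmer.

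The cost is a few lines of SAP text, a small programming change and one sensitivity analysis. PFS-1 and DOR may come out slightly shorter; no other endpoint changes.
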